3.2 Study Population

3.2.1 Sources of Patients. Patients will be approached for inclusion into LABS-1 and LABS-2 at the MeritCare Bariatric Surgery Department, Fargo ND, at the University of Pittsburgh Medical Center and at Cornell/Columbia Medical Center in New York. LABS-3 Psychosocial participants will be selected from those individuals participating in LABS-1 and LABS-2.

3.2.2 Inclusion Criteria

- Male and female patients at least 18 years of age who undergo bariatric surgery by a LABS-certified surgeon.
- Previous enrollment in LABS-1 and LABS-2.
- BMI of greater than or equal to 35.

3.2.3 Exclusion Criteria

- Informed consent not obtained
- Type 1 Diabetes Mellitus
- Unlikely to comply with follow-up protocol (ie: geographically inaccessible for study visits)
- Unable to communicate with local study staff

3.2.4 Criteria for Study Withdrawal

- Patient withdraws consent
- The Principal Investigator or NIDDK ends the study

3.3 Enrollment Procedures. Once a candidate for LABS-3 Psychosocial has been identified, study details will be carefully discussed with the patient by a member of the LABS staff. All study related procedures will be explained and questions about the research protocol will be answered. If the patient agrees to participate, the study coordinator or Principal Investigator will go through the informed consent process with the patient. The patient will be asked questions to assure a thorough understanding of the consent document. Once a patient has consented to LABS-3 Psychosocial, they will be enrolled into the protocol.

3.4 Study Visits and Database Contents. Patients will be scheduled 1-30 days prior to surgery for their LABS-3 Psychosocial baseline evaluation at the Neuropsychiatric Research Institute, at the University of Pittsburgh Medical Center and at Cornell/Columbia in New York. Complete follow-up data collection will occur at approximately 12 months, and annually following surgery, along with a brief follow up assessments at 6 months and 18

months following surgery. There will also be data collected about weight loss, and psychological and quality of life measures that will be obtained from the LABS-2 database. All data are collected during an in-person visit, by phone assessment, or by accessing the LABS-2 data set. The tables below indicate the schedule of measures by study visit. A copy of all measures is included in the Appendix. New measures/ tasks are being incorporated for one time administration at the 7 year follow up time point. The new measures/ task will be accessible online for participant convenience which allows for the ability to complete these at home.

3.4.1 Clinical Forms and Interview Schedule

Measure/Test	Form Details	Baseline/ Presurgery	6 month follow up	12 month follow up	18 month follow up	annual follow up
PSYCHOPATHOLOGY N= 250						
INTERVIEW						
SCID/IP	Structured Clinical Interview for DSM-IV	X				X
EDE- BSV	Eating Disorders Examination- Bariatric Surgery Version	X		X		X
M-FED-BSV	MFED- Bariatric Surgery Version	X	X	X	X	
SELF-REPORT						
BDI*	Beck Depression Inventory	X	X	X		X
SF-36*	Short Form-36	X	X	X		X
IWQOL- Lite	Impact of Weight on Quality of Life- Lite	X*	X	X*		X*
PETS	Psychiatric and Emotional Test Survey	* X	X	* X	X	* X
MED	Medication Form	* X	* X	* X	X	* X
CTQ	Childhood Trauma Questionnaire					X (one time)
EATING BEHAVIOR N= 100						
NDS	48 Hour Dietary Recall- Nutritional Data System	X	X	X		X

* Gathered as a part of LABS-2

INTERVIEW SCHEDULE WITH NEW MEASURES AND TASKS AT YEAR 7:

LABS Baseline and F/U Funding for Part of Cohort						RO1 Funding				
	Pre-surg	6 mo	1 yr	18 mo	2 yrs	3 yrs	4 yrs	5 yrs	6 yrs	7 yrs
INTERVIEW										
SCID/IP	X				X	X	X	X	X	X
EDE-BSV	X		X		X	X	X	X	X	X
M-FED-BSV		X	X	X	X	X	X	X	X	X
72-hour dietary recall (NDS-R)	X	X	X		X	X	X	X	X	X
SELF-REPORT										
Administered as a part of LABS 2*	X	X	X	X	X	X	X	X	X	X
The following have been added as a new, separate final visit.										
DERS										X
AIM										X
UPPS-P										X
ATQ-ECS										X
SPSRQ										X
Go/No-Go Task										X
Delay Discounting Task										X

3.4.2 Interview Description

- Structured Clinical Interview for DSM-IV, Patients Edition (SCID-IP; First, et al., 2001). The SCID-P is a widely used semi-structured interview that will be administered to assess comorbid Axis I disorders. Further, an impulse control module will be administered to assess impulsive/compulsive disorders for participants at their 72 month visit and beyond. A review of reliability studies for the SCID found kappa coefficients (measures of inter-rater reliability) ranging from .03 to 1.00, although the majority of the studies found kappas in the range of .7 to .8; test-retest coefficients ranged from .37 to .89.
- M-FED Bariatric Surgery Version (M-FED-BSV). Data will be obtained on other treatment received using the M-FED, an instrument designed for this purpose that has been used in several multi-center BN treatment and longitudinal studies (See for example, Mitchell, et al., 2002; Crow, et al., 2002). A modified version is available for bariatric surgery patients (M-FED-BSV).
- Eating Disorder Examination (EDE-BSV; Fairburn & Cooper, 2006). The diagnostic version of the EDE will be used as the primary measure of eating behavior and pathology. The EDE is an investigator-administered interview used to assess current eating disorder symptoms. The EDE contains four subscales (Restraint, Eating Concern, Shape Concern, and Weight Concern) associated with core psychopathology of eating disorders, as well as frequency measure of binge eating and compensatory behavior. The

validity and reliability of the EDE have been well documented (Fairburn & Cooper, 1993). We have modified a version of the EDE for use with bariatric surgery patient and this form will be used (EDE-Bariatric Surgery Version, EDE-BSV). The modified version of the EDE quantifies eating behavior, experiences of plugging and dumping syndrome, binge eating, grazing, compensatory behaviors, such as vomiting, and chewing and spitting food. This version includes assessment of night eating and excessive fluid intake. The modified version of the EDE has been used in gathering data on eating behaviors in RYGBP patients in prior studies.

3.4.3 Self-Report Description

- Beck Depression Inventory. (BDI; Beck et al, 1961). The BDI is a 21-item instrument that is widely used to assess depressive symptoms. A meta-analysis of reliability studies found mean coefficient alphas of .86 (psychiatric patients) and .81 (non-psychiatric patients). In addition, the BDI has been found to correlate highly with other measures of depression, and discriminate between groups of individuals with and without depression.
- ShortForm-36 (SF-36, Stewart & Ware, 1992). The SF-36 is a 36-item questionnaire that assesses functioning and quality of life as it relates to health status. The SF-36 assesses health status in 8 areas: physical functioning, physical role limitations, emotional role limitations, bodily pain, general mental health, vitality and general health perceptions. Composite scores for physical and mental functioning are also available. Test-retest reliabilities on the SF-36 scales range from .68 (social functioning) to .93 (physical functioning). The test-retest reliabilities for physical and emotional composite scores are .92 and .88 respectively. A variety of studies have established the validity of the SF-36 across different patients and cultural populations.
- Impact of Weight on Quality of Life Questionnaire (IWQOL-Lite; Kolotkin, et al 2001; Kolotkin et al, 2002). This is a 31-item, self-report, obesity-specific quality of life measure. The IWQOL-Lite provides five subscales (Physical Function, Self-Esteem, Sexual Life, Public Distress, Work) and a total score. Scores on the IWQOL-Lite range from 0 to 100, with 100 representing the best and 0 the most impaired quality of life. In previous studies the IWQOL-Lite has demonstrated excellent psychometric properties: internal consistency ranged from 0.90 to 0.94 for scales and was 0.96 for total score; test-retest reliability ranged from 0.81 to 0.94 for total score; the scale structure was confirmed by factor analysis; there was good support for construct validity in that scales correlated well with BMI, weight loss, treatment-seeking status, and appropriate collateral measures. The 31-item IWQOL will be administered intact, along with additional quality of life questions specific to bariatric surgery patients. Additional items will include eating-related problems such as involuntary and voluntary vomiting, plugging, and dumping, physical symptoms such as diarrhea, heartburn, bloating, and abdominal pain, and psychosocial variables such as issues related to appearance, changes in marital relationships and friendships, increased feelings of vulnerability, establishing new eating behavior, and coping with stress without food. Psychometric analyses will be performed to derive one or more bariatric surgery-specific quality of life scales.
- Psychiatric and Emotional Test Survey: (PETS) This questionnaire was developed by the LABS consortium to collect psychiatric and emotional health information on patients enrolled in LABS.

- Medication Form: (MED) This questionnaire was developed by the LABS consortium to collect medication and supplement use on patients enrolled in LABS.
- Childhood Trauma Questionnaire (CTQ) This 28-item self-report is useful with individuals referred for a broad range of psychiatric symptoms and problems, including: Post-traumatic stress disorder, Depression, Eating disorders, Addictions, Suicide attempts, Personality disorders and Sexual problems. As a part of the LABS 3 protocol, this questionnaire will only be administered one time at the participants next scheduled annual follow up.

3.4.4 Eating Behavior Assessment Description

- The NDS-R is a windows-based nutrient calculation system which allows for the detailed assessment specific of food intake over a 24-hour time intervals. The NDS-R was released by the Nutrition Coordinating Center in the Division of Epidemiology and School of Public Health at the University of Minnesota. Over 800 dietary interviewers have been trained in this system. The NDS-R is administered as a telephone interview or face-to-face, is typically administered in the evening, and data from it are entered directly into a computer. The NDS-R system contains over 18,000 foods and 8,000 brand name products, including many ethnic foods. The system has been used widely in nutrient research (e.g. Shakel, Sievert & Buzzard, 1988; Feskanich et al., 1999). It is considered the gold standard method of assessment of food intake. The NDS-R has been used successfully with overweight and obese samples (Yaroch, Resnicow, Petty, & Khan, 2000; Djuric, DiLaura, Jenkins, Darga, Jen, Mood, et al. 2002; Ebbeling, Sinclair, Pereira, Garcia-Lago, Feldman, Ludwig, 2004; Quatromoni, Copenhafer, D'Agostino, & Millen, 2002).

3.4.5 New Self-Report Measures/Computer Tasks for Psychopathology Dimensions

- The measures outlined below have been added to be assessed at the final assessment time point (year 7). The self-report measures and computer tasks will administered via the web using software from Millisecond Software using the Inquisit 4 program.
- Difficulties in Emotion Regulation Scale (DERS; Gratz & Roemer, 2004). The DERS is a 36-item self-report questionnaire that assesses six domains of emotion dysregulation (i.e., non-acceptance of negative emotions, inability to engage in goal-directed behavior when distressed, difficulties controlling impulsive behavior when distressed, limited access to effective emotion regulation strategies, lack of emotional awareness, lack of emotional clarity) and has been found to have acceptable internal consistency as well as adequate test-retest reliability and construct validity (Gratz & Roemer, 2004).
- Affect Intensity Measure (AIM; Larsen & Diener, 1987). The AIM is a 40-item self-report measure of positive and negative emotional intensity and reactivity. Evidence supports the reliability and validity of the measure (Larsen & Diener, 1987; Bryant et al., 1996).
- UPPS-P Impulsive Behavior Scale (UPPS-P; Cyders & Smith, 2007). This is a 59-item self-report measure assessing five dimensions of impulsivity. Only the negative urgency and positive urgency subscales will be administered. The measure has demonstrated good internal consistency and validity (Cyders & Smith, 2007).

- Effortful Control Scale of the Adult Temperament Questionnaire (ATQ-ECS; Evans & Rothbart, 2007). This 19-item self-report measure assesses several components of dispositional effortful control, including attentional control (i.e., ability to voluntarily focus or shift attention), inhibitory control (i.e., ability to inhibit behavior), and activation control (i.e., ability to activate behavior as needed). The measure has evidenced good reliability and validity (Evans & Rothbart, 2007).
- Sensitivity to Punishment and Sensitivity to Reward Questionnaire (SPSRQ; Torrubia et al., 2001). This is a 44-item self-report measure that is based on Gray's behavioral inhibition and activation motivational systems conceptualization, and assesses sensitivity to punishment and reward. The measure has demonstrated adequate internal consistency, test-retest reliability, and construct validity (Torrubia et al., 2001). Only the Sensitivity to Reward subscale of the measure will be administered.
- Go/No-Go Task (Osman et al., 1992). This computerized task assesses the capacity for suppressing previously reinforced responses. Participants are asked to quickly respond to a target stimulus (e.g., letter A) and to inhibit responding to other stimuli (e.g., letters B, D, E, etc.). The target stimulus is presented more frequently to establish a learned (prepotent) response, thus requiring an inhibition process to not respond to an incorrect stimulus. The index of inhibitory control will be the number of mistaken responses (commission errors) made on No-Go trials.
- Delay Discounting Task (Kirby et al., 2000; Kishhinevsky et al., 2012). Delay discounting tasks require participants to choose between receiving a larger amount of money after a delay versus receiving a smaller amount immediately. The size of the smaller immediate reward is adjusted based on previous responses, narrowing the range of choices until an indifference point (i.e., amount at which the smaller more immediate reinforcer and larger delayed reinforcer are judged as being of equal value) is determined for each delay interval.

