**Longitudinal Assessment of Bariatric Surgery (LABS-3):
Psychosocial Issues and Bariatric Surgery**

Design Synopsis

Hypotheses

1. Patients undergoing bariatric surgery will experience significant decreases in the rates of psychopathology, in particular depressive illness, and significant improvements in quality of life, post-operatively.
2. Untreated psychopathology that persists well beyond the surgery (e.g. to one-year follow-up) or that develops post-operatively will be associated with less weight loss and decreased quality of life.
3. Untreated psychopathology at the time of bariatric surgery, including affective disorders and substance abuse/alcohol abuse will be associated with increased short-term (e.g. 90 day) complications (e.g. problems with plugging, vomiting, and dehydration)
4. Syndromal/subsyndromal eating disorders prior to surgery including binge eating disorder and night eating syndrome will be associated with eating disorder symptoms and less weight loss at long-term follow-up.
5. Greater levels of affect dysregulation, greater deficits in cognitive control and greater deficits in reward processing will be associated with less favorable outcomes (higher affective disorder rates, less favorable net weight change, and increased eating disorder pathology/alcohol use pathology) following surgery.

Type of Study

- Prospective cohort study done at three (3) LABS centers.

Inclusion Criteria

- Male and female patients who are at least 18 years of age and undergo bariatric surgery by a LABS certified surgeon.
- Previous enrollment in LABS-1 and LABS-2.
- BMI at baseline of greater than or equal to 35.

Exclusion Criteria

- Informed consent not obtained
- Type 1 Diabetes Mellitus
- Unlikely to comply with follow-up protocol (ie: geographically inaccessible for study visits)
- Unable to communicate with local study staff

Sample Size

- In order to sample a sufficient number of subjects with significant psychopathology at baseline, the sample size for the assessment of psychopathology is 250. The assessment of eating behavior will be done on a subset of 100 subjects.

Duration of Follow-up

- Up to 7 years following bariatric surgery

Outcomes

- Changes in medical and psychosocial measures

Data Collection Schedule

- The LABS-3 Psychosocial baseline data will be collected within 30 days prior to bariatric surgery.

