3.4.6 Other Forms

- The **Off-Protocol Form** will be completed by the study coordinator to report deviation(s) from study protocol (e.g., missed visit, incomplete data collection).
- An **Inactivation Form** will be utilized to report patient drop-outs or inactivations and reason(s) for dropping out or inactivation.
- An **Enrollment Form** will be completed to report those participants who are enrolled into LABS-3 Psychosocial. This form reports whether patients provided consent to LABS-3 Psychosocial, along with dates of consent. If the patient does not consent, the reason why is reported.

4 Data Analysis and Statistical Power

Statistical Analyses

1. Preliminary Analysis
 - a. Descriptive Statistics. Descriptive statistics (e.g., means, standard deviations, ranges, frequency distributions) at each assessment point will be performed on all demographic,

psychopathology (SCID-I, BDI), eating behavior (EDE-BSV, NDS) and quality of life (SF-36, IWQOL-Lite) measures.

b. Site Comparisons. Baseline comparisons between sites will be made on demographic, psychopathology, eating behavior and quality of life measures using ANOVA for continuously distributed measures, Kruskal-Wallis for ordinal or continuous non-normal measures, and chi-square tests for nominal measures.

c. Missing Data Analysis. A pattern mixture model (Little, 1993; 1994; 1995; Hedeker & Gibbons, 1997) based on a random regression model (RRM) (Gibbons, et al., 1993) will be used to examine the impact of missing data pattern on longitudinal eating-related variables, weight loss, quality of life, and depressive symptomatology. Subjects will be divided logically into groups based on their missing data pattern following the guidelines provided by Hedeker & Gibbons (1997). These groups will then be included as a between-subjects factor and the impact of this factor on the trajectory of outcome measures will be evaluated. This will provide a determination of the extent to which trajectories depend on the pattern of missing data.

2. Hypothesis Testing

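### The Go/No-Go index counts only No-Go commission errors, so it cannot tell good inhibition from not responding

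*Protocol*

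**What the plan says.** Section 3.4.5 of the protocol describes the task. On the instruction: "Participants are asked to quickly respond to a target stimulus (e.g., letter A) and to inhibit responding to other stimuli". On the design: "The target stimulus is presented more frequently to establish a learned (prepotent) response". On the score: "The index of inhibitory control will be the number of mistaken responses (commission errors) made on No-Go trials". It gives no number of Go or No-Go trials, and neither Go hits nor Go omissions enter the score.

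On administration, section 3.4.5 states: "The self-report measures and computer tasks will administered via the web using software from Millisecond Software using the Inquisit 4 program". Section 3.4 adds: "The new measures/ task will be accessible online for participant convenience which allows for the ability to complete these at home". The schedule in section 3.4.1 introduces the year-7 block with "The following have been added as a new, separate final visit", and the measures are given once.

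The score serves Hypothesis 5 in the Design Synopsis, which expects that "greater deficits in cognitive control and greater deficits in reward processing will be associated with less favorable outcomes". Section 3.4.6 provides an Off-Protocol Form "to report deviation(s) from study protocol (e.g., missed visit, incomplete data collection"), but attaches no scoring consequence to it.

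**The concern.** By the protocol's own account, the task measures inhibition of a response that frequent targets have made habitual. A low commission count shows inhibition only if the participant was responding to targets. The index never checks this, so withholding by effort and withholding by inattention get the same score.

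The error has one direction. Not responding can only remove commission errors, so disengaged participants move toward the good end of the scale whatever their true control. When Hypothesis 5 is examined, these misplaced records dilute any real association between poor inhibitory control and poor outcome. The task is taken once, so no repeat run would expose a bad one.

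**Working it through.** The protocol states no figure for this task, so there is nothing to reproduce. The check has three steps.

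**1. Consequence of the definition**

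Let K be the number of No-Go trials, e the commission-error rate while engaged, and f the fraction of the task the participant engages with. Then

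expected count = K × f × e.

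At f = 0 the count is exactly 0 for every K and e. This needs no assumption.

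**2. Part-way disengagement**

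K, f and e are assumptions. Take an impulsive participant with e = 0.40 and K = 50:

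| f | K × f × e | Expected count |
|---|---|---|
| 1 | 50 × 1 × 0.40 | 20 |
| 0.5 | 50 × 0.5 × 0.40 | 10 |
| 0.25 | 50 × 0.25 × 0.40 | 5 |
| 0.1 | 50 × 0.1 × 0.40 | 2 |
| 0 | 50 × 0 × 0.40 | 0 |

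Compare this person with a careful participant who completes the task with e = 0.10. The binomial probability that the impulsive one has strictly fewer errors is:

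| f | K = 50 | Range over K = 20, 50, 100 |
|---|---|---|
| 0 | 0.995 | 0.88 to 1.00 |
| 0.1 | 0.855 | 0.66 to 0.96 |
| 0.25 | 0.446 | 0.37 to 0.45 |
| 0.5 | 0.046 | 0.01 to 0.11 |
| 1 | below 0.001 | at most 0.006 |

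The f = 0 entry for K = 50 can be checked by hand: it is the chance that the careful participant makes at least one error, 1 − 0.90^50 = 0.995. The count always moves toward better control. The best score is certain only with no responding at all, and the ranking reverses reliably only with very little engagement.

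**3. Effect on an association**

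All inputs here are assumptions:
- a standard normal trait with true trait-outcome correlation .30, and n = 100;
- No-Go errors binomial with logit(error probability) = −1.2 + 0.8 × trait, and K between 20 and 60;
- a random 5% or 15% of participants, unrelated to the trait, replaced by non-responders with error probability .01.

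Mean correlation between count and outcome:

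| Disengaged | All engaged | With non-responders | Attenuation |
|---|---|---|---|
| 5% | about .24 to .27 | about .23 to .25 | about 7 to 9% |
| 15% | about .24 to .27 | about .19 to .21 | about 19 to 22% |

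Setting the disengaged sessions to missing brings the mean correlation back to about .24 to .27.

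**The case against.** The strongest reply is that this is a short description of a measure, and that rules on valid sessions usually sit in a statistical analysis plan, which is not shown here. Nothing in the protocol forbids excluding invalid runs. That reply stands for the missing completion and validity rules taken alone. It does not remove the point, because the protocol does state the index, and the stated index uses no Go-trial information.

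The size can also be disputed, fairly. Trial counts, error rates, disengagement rates, the .30 and the n of 100 are all assumed. At 5% disengaged the loss is about .02 in the correlation, against a sampling standard error near .10 at n = 100. The Effortful Control Scale also covers inhibitory control, so Hypothesis 5 does not rest on this task alone. Section 4 gives no analysis for that hypothesis.

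A reader might infer more than the documents support:
- **That early quitters score best.** Stopping part-way lowers the count without making it the lowest. For a session that breaks off, even this requires the partial run to be scored as it stands. The protocol does not say so, and it logs incomplete collection as a deviation.
- **That the task is unsupervised.** Home completion is an option. Supervision is not described either way, and the schedule speaks of a visit.
- **That slow responders gain.** No response window or deadline is given.
- **That those with the poorest control disengage most.** This would enlarge the bias, but the documents do not say it and the figures above do not assume it.

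**Conclusion.** The point holds in a narrow form. The index fixed in section 3.4.5 cannot separate inhibition from non-responding. A participant who does not respond receives the best possible score, and one who disengages part-way is scored as better controlled than they are. The first statement is exact. The second gives a direction whose size depends on how much of the task was engaged with.

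If disengagement is unrelated to the trait, the Hypothesis 5 association is pulled toward zero, by about 8% with 5% disengaged and about 20% with 15%. These percentages illustrate the mechanism and do not estimate what will happen in this study, since the protocol supplies none of the inputs. Severity is minor: one score among several one-time year-7 measures is affected, and the repair is cheap.

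**What to change.** Amend the scoring sentence in section 3.4.5 so that:
- commission errors are scored only for completed sessions that meet a minimum Go-trial hit rate set before the data are examined;
- sessions that fail either condition are treated as missing, not as zero errors;
- Go omissions are reported beside the commission count.

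A d-prime that combines Go hits and No-Go errors can serve as a sensitivity index.

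If partial runs are ever scored, use errors divided by No-Go trials presented. A rate alone is not enough. Among completers with the same K it is the count divided by a constant, and a participant who finishes without responding still scores 0/K = 0. The Go-trial criterion deals with that case. Mean Go response time need not be added as a covariate: fast responding may itself be part of impulsivity, and adjusting for it could remove signal.

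The change needs no new visit, task or participant time, provided Go-trial responses are recorded. The cost is that a few sessions become missing.
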